#### 6.2.2 Formulation, Packaging, and Labeling

#### Live Influenza Virus RG-A/Texas/71/2017 (H3N2)

The final product was vialed at approximately 1.86 X 10^6 TCID50/mL of Influenza A Human Challenge Virus (H3N2) in 1X SPG (7.4% sucrose, 3.8 mM KH2PO4, 7.2 mM K2HPO4, 5.4 mM L-glutamic acid). Each vial has a fill volume of 0.6 mL.

Each vial was individually labeled with the product name, description, and caution statement. The label was affixed to 2 mL cryogenic vials prior to final fill with Live Influenza Virus RG-A/Texas/71/2017 (H3N2) Virus [Charles River Laboratories, Malvern PA] (Lot #1507-232149).

#### Diluent and Sham Product

1X SPG (7.4% sucrose, 3.8 mM KH2PO4, 7.2 mM K2HPO4, 5.4 mM L-glutamic acid). Each vial has a fill volume of 1.2 mL. The diluent will also be used as a sham inoculum. Each vial was individually labeled with the product name, description, and caution statement. The label was affixed to 2 mL cryogenic vials prior to final fill with 1X SPG [Charles River Laboratories, Malvern PA] (Lot #141701).

#### 6.2.3 **Product Storage and Stability**

#### Live Influenza Virus RG-A/Texas/71/2017 (H3N2)

The human challenge virus will be shipped to the sites and stored at  $\leq$  -65°C in single-use vials. Additional details of product storage and stability can be found in the MOP.

#### Diluent/Sham Product

The 1X SPG will be shipped to the sites and stored at  $-20^{\circ}C \pm 10^{\circ}C$  in single-use vials. Additional details of product storage and stability can be found in the MOP.

MAD NasalTM Intranasal Mucosal Atomization Device (Teleflex, Morrisville NC)

The MAD NasalTM Intranasal Mucosal Atomization Device (Teleflex, Morrisville NC) will be stored at room temperature (15-30°C).

#### 6.2.4 **Preparation and Administration**

#### Live Influenza Virus RG-A/Texas/71/2017 (H3N2)

The Live Influenza Virus RG-A/Texas/71/2017 (H3N2) is an infectious influenza virus and requires handling at Biosafety Level 2. All steps in preparing the syringes should be performed with aseptic technique in a biosafety cabinet.

The challenge virus will be administered intranasally, 0.5 mL in each nostril of a recumbent participant using the MAD NasalTM Intranasal Mucosal Atomization Device attached to a 1 mL

syringe. Detailed instructions for challenge virus inoculum preparation and administration are provided in the MOP.

## 6.3 Measures to Minimize Bias: Randomization and Blinding

#### 6.3.1 Study Product Assignment Procedures

Subjects will be randomized to receive either Live Influenza Virus RG-A/Texas/71/2017 (H3N2) challenge virus or sham placebo within each challenge dose group. Subject will receive one of three doses of challenge virus depending upon the challenge cohort into which they enroll using the adaptive trial design. The ratio of subjects randomized to receive either challenge virus or sham placebo is described below.

Challenge	Challenge Dose Group	Challenge virus:Sham
Cohort		placebo
1A, 1B, 1C	10  TCID 50	Targeted 12:1
2A, 2B, 2C	10  TCID 50	Targeted 12:1
3A, 3B	10  TCID 50	Targeted 17:1

#### 6.3.2 Randomization and Blinding

Eligible subjects for each challenge cohort will be randomized to receive either challenge virus or sham. Enrollment into the active challenge cohort will be completed before the next challenge cohort is opened to enrollment. The subsequent challenge cohort will be selected and opened for enrollment after safety review, as shown in **Figure 1**. To compress the overall dosing timelines, challenge cohorts may be split between the 2 sites. Subjects that drop out less than 48 hours prior to challenge will not be replaced, but additional randomization slots will be included (at the same targeted allocation ratios for each cohort) to allow for the possibility of enrollment beyond the targeted cohort sizes.

The list of randomized treatment assignments will be prepared by statisticians at The Emmes Company, LLC. and included in the enrollment module of Emmes' Internet Data Entry System (IDES). IDES will assign each subject a treatment code from the list after demographic and eligibility data have been entered into the system. A designated individual at each site will be provided with a treatment key, which links the treatment code to the actual treatment assignment, which will be kept in a secure place.

Instructions for use of the enrollment module are included in the IDES User's Guide. Manual back-up randomization procedures are provided in the MOP for use in the event that the site temporarily loses access to the Internet or the online enrollment system is unavailable.

#### 6.3.3 Blinding and Masking Procedures

Study product will be prepared by an unblinded pharmacist but administered by a blinded administrator. The subjects, the study personnel who perform study assessments after administration, data entry personnel at the sites, and laboratory personnel performing immunologic assays will be blinded to treatment assignment. The SMC will receive data in aggregate by cohort and challenge dose group, and they may be unblinded to individual study product assignments, as needed, to adequately assess safety issues. Refer to the MOP for unblinding procedures.

## 6.4 Study Intervention Compliance

Subjects will be directly observed at the time of dosing by a member of the clinical research team who is licensed to administer the study product. Administration will be documented on the Treatment Administration Record and entered into the eCRF.

## 6.5 Concomitant Therapy

All concomitant medications taken within 90 days prior to signing the ICF will be reviewed with subjects to determine stability of chronic diseases and eligibility. Medications reported in the eCRF are limited to those taken within 30 days prior to challenge. Concomitant medications will be reviewed at every study visit through the end of the study. Women of childbearing potential in a heterosexual relationship must agree to use true abstinence or use at least one acceptable primary form of contraception through the end of the study.

Receipt of any influenza vaccine during the 2019/2020 and/or 2020/2021 influenza vaccine seasons, regardless of the date of receipt, will be documented. Subject receipt of non-seasonal influenza vaccine, including those that are experimental, product type, vaccine virus strains and approximate date of previous two season's vaccination will be documented. Prior participation in any influenza challenge study will be documented. Note that prior enrollment in any influenza challenge study within the prior two years and/or receipt of any influenza vaccine four months prior to challenge is exclusionary.

The following prescription or over-the-counter medications cannot be used within 7 days prior to admission to and through the confinement period, unless approved by the investigator: oseltamivir, zanamivir, peramivir, baloxavir marboxil, amantadine (generic) and rimantadine (Flumadine and generic), aspirin, intranasal steroids, decongestants, antihistamines, and other non-steroidal anti-inflammatory drugs (NSAIDs).

Subjects who use asthma medications including inhaled, oral, or IV corticosteroids, leukotriene modifiers, long and short acting beta agonists, theophylline, ipratropium, biologics, will be excluded from the study.

Any medications that may be associated with impaired immune responsiveness including, but not limited to, corticosteroids exceeding 10 mg/day of prednisone equivalent, allergy injections, immunoglobulin, interferon, immunomodulators, cytotoxic drugs, or systemic corticosteroids or other similar or toxic drugs cannot be used during the preceding 12-month period prior to screening. Low dose topical and intranasal steroid preparations used for a discrete period of time are permitted.

Subjects should not have received any investigational drug/investigational vaccine/licensed vaccine within 30 days prior to the planned date of challenge, with the exception of an EUA authorized or licensed COVID-19 vaccine product  $\geq$  two weeks prior to admission.

Protocol 20-0005	Version 8.0
H3N2 Dose-Ranging Challenge	04May2023

Subjects should not have received influenza vaccine four months prior to challenge and must not plan to receive an influenza vaccine during the study period (approximately 57 days).

Subjects should not have received blood or blood products during the six months prior to the planned date of challenge.

#### 6.5.1 Non-Research Standard of Care

Oseltamivir phosphate (TAMIFLU®) or baloxavir marboxil (XOFLUZA™) will be offered to any subject who has not had two consecutive days of negative qualitative RT-PCR tests for influenza virus by Study Day 8. Oseltamivir is a neuraminidase inhibitor indicated for the treatment of acute uncomplicated influenza A and B in patients 2 weeks of age and older who have been symptomatic for no more than 2 days, and for prophylaxis of influenza in patients 1 year and older. Baloxavir is a polymerase acidic (PA) endonuclease inhibitor indicated for the treatment of acute uncomplicated influenza in patients 12 years and older who have been symptomatic for no more than 48 hours.

Subjects who continue to shed virus beyond Day 8 will undergo routine daily evaluations as described in Sections 5 and 8. The licensed study clinician listed on the Form FDA 1572 may also treat the subject with symptom-directed, over-the-counter therapies as permitted by the study protocol. If the subject meets criteria for escalation of care, evaluation and treatment will be at the discretion of the consulting physician. Escalation of care may result from the development of serious related or unrelated signs or symptoms during confinement period.

## 7. STUDY INTERVENTION DISCONTINUATION AND PARTICIPANT DISCONTINUATION/WITHDRAWAL

## 7.1 Halting Criteria and Discontinuation of Study Intervention

#### 7.1.1 Study Halting Criteria

Additional enrollment and interventions/administration of study products will be paused for Safety Monitoring Committee (SMC) review/recommendation if any of the following events are reported:

- 1. Any subject experiences laryngospasm, bronchospasm, or anaphylaxis within one day after challenge.
- 2. Two or more subjects experience generalized urticaria (defined as occurring at more than two body parts) within three days after challenge.
- 3. Any subject experiences a related SAE during the confinement unit period.
  - This includes any subject who develops a severe influenza complication (Section 2.3.1) during the confinement unit period and requires admission to an Intensive Care Unit (ICU), and/or receipt of ICU level of care
- 4. Two or more subjects per challenge cohort (or four or more subjects per dosing group) experience the same related grade 3 AE of any kind after challenge through the confinement unit period and related to study product.
- 5. Any medically significant safety issue that the PI determines should halt the study.

The SMC is external to the DMID and comprises at least 3 voting members. The SMC will consist of members with appropriate expertise to contribute to the interpretation of the data from this study. Its activities will be delineated in a SMC charter that will describe the membership, responsibilities, and the scope and frequency of data reviews. The SMC will operate on a conflict-free basis independently of the study team. The DMID or the SMC may convene ad hoc meetings of the SMC according to protocol criteria or if there are concerns that arise during the study.

As defined in the charter, the SMC will review data at specified times during the course of the study for subject and overall study progress and will conduct ad hoc reviews as appropriate when a halting rule is met or for immediate concerns regarding observations during this study. The SMC will hold the following meetings; an organizational meeting prior to subject enrollment, any ad hoc meetings when a halting rule is met or due to specific safety issues as the SMC deems necessary, and a final meeting to review cumulative safety data.

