### Safety Threshold

The safety threshold is defined as meeting one of the protocol-defined halting criteria outlined in Section 7.1.1 which includes the occurrence of severe influenza complications in any study subject (Section 2.3.1). If a subject has a severe influenza complication(s), the study staff and subject will be unblinded as to receipt of challenge virus or sham and as to the results of influenza RT-PCR testing for safety evaluation and potential therapeutic intervention with an approved influenza antiviral agent.

In this adaptive schema, the initial cohort (Cohort 1A) for the lowest challenge dose group will include a targeted total of 12 subjects receiving 10^4 TCID50 of the challenge strain and one subject receiving sham placebo. If fewer than 80% of subjects meet the case definition for influenza in Cohort 1A, the dose will escalate to 10^5 TCID50 to include Cohort 2A. If 80% or more subjects in Cohort 1A meet the case definition for influenza, the lowest challenge dose group will be expanded to include a targeted total of 12 additional subjects receiving 10^4 TCID50 of the challenge strain and one subject receiving sham placebo to comprise Cohort 1B. Cumulatively, if fewer than 80% of subjects in Cohorts 1A and 1B meet the case definition for influenza, the dose will escalate to 10^5 TCID50 to include Cohort 2A. If 80% or more of the subjects in Cohorts 1A and 1B meet the case definition for influenza than the lowest challenge dose group will be expanded to include a targeted total of 12 additional subjects receiving 10^4 TCID50 of the challenge strain and one subject receiving sham placebo to comprise Cohort 1C. Cumulatively, if fewer than 80% of subjects in Cohorts 1A, 1B, and 1C meet the case definition for influenza the dose will escalate to 10^5 TCID50 to include Cohort 2A. If 80% or more of the subjects in Cohorts 1A, 1B, and 1C combined meet the case definition for influenza then the optimal dose of 10^4 TCID50 will be selected.

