The  $10^5$  TCID50 challenge dose group similarly includes up to three cohorts each with a targeted total of 12 subjects receiving  $10^5$  TCID50 of the challenge strain and one subject receiving sham placebo with the thresholds for dose escalation to  $10^6$  TCID50 being < 70% subjects for Cohorts 2A, 2B, and 2C cumulatively moving from Cohort 2A to Cohort 2B and Cohort 2C, respectively. The highest challenge dose group to be evaluated in this study is  $10^6$ 

Protocol 20-0005	Version 8.0
H3N2 Dose-Ranging Challenge	04May2023

TCID50, with each of two challenge cohorts including a targeted total of 17 subjects receiving  $10^6$  TCID50 of the challenge strain and one subject receiving sham placebo.

Following virus challenge, subjects will be monitored daily for up to 7 days post-challenge (Days 2-8). During this confinement period, time-series collections of biological samples and clinical information will occur daily from pre-challenge (baseline) through Study Day 8. The different specimen types and clinical assessments are shown in (Table 1). Whole blood samples will be processed into component parts (e.g., PBMCs, plasma, sera, RNA, DNA) to evaluate multiple host response systems including the immune, molecular, and cellular responses in the circulation and nasal mucosa. Additionally, subjects will be provided wearable devices for continuous monitoring of physiological measures including heart rate, ECG, body temperature, and sleep habits.

Examples of the devices used in the study include those listed below. Other devices approved for consumer and/or clinical use may also be used, provided they are fully non-invasive and do not present any additional risk to study subjects:

• Garmin Vivosmart 4: This commercially available product is intended for training and recreational use. It is worn on the wrist and uses photoplethysmography (PPG) technology along with mechanical sensors to measure heart rate, oxygen saturation, activity, etc. The Garmin will transfer the subject's data via Bluetooth to the smartphone where the compatible app has been installed. These apps will then upload the data to cloud-based servers maintained by the individual device manufacturers. Data will then be uploaded to a secure server at the study sites.

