## 4.3 Justification for Dose

Protocol 20-0005	Version 8.0
H3N2 Dose-Ranging Challenge	04May2023

Subjects will be randomized and administered a single challenge dose of either sham placebo or a virus dose between  $10^4$  to  $10^6$  TCID50. Historically, a  $10^4$  TCID50 has been safely used as the lowest dose tested in challenge studies[5-7]. There is no indication from non-clinical studies of the recombinant influenza A/Texas/71/2017 (H3N2), clade 3C3a virus in mouse, hamster and ferret models of infection that this virus will behave any differently in humans than the wild-type parent influenza virus.

The dosing plan will follow an adaptive dose escalation schedule (**Figure 1**) that will include up to three different challenge dosing groups. This dosing plan is designed to optimize subject safety, starting with a low dose and allowing flexibility to make informed adjustments between challenge cohorts from outcome results of the previous challenge cohort. The plan is guided by our experience and the results of our 3 previous human titration studies.

For the first exposure in humans, the initial low dose challenge will be conducted in a group of a targeted total of 12 subjects (and 1 sham) to assure the virus is safe with no study-related or unanticipated adverse events observed or reported. Dose escalation to the next dose level and subsequent higher doses, if necessary, will be informed by both safety and AR outcomes given a pre-specified decision algorithm for dose-escalating. The decision to escalate or not escalate to the next challenge dose will involve the following criteria:

- The tested dose is determined to be safe with no occurrence of halting criteria or severe influenza complications
- An AR < 80% triggers dose escalation in the 10^4 TCID50 challenge dose group.
- An AR < 70% triggers dose escalation in the  $10^5$  TCID50 challenge dose group.
- An AR  $\ge$  80% in the 10^4 TCID50 challenge dose group would stop escalation, and a repeat of the presumed optimal dose for up to 3 total challenge cohorts: 1A, 1B and 1C.
- An AR  $\geq$  70% in the 10^5 TCID50 challenge dose group would stop escalation, and a repeat of the presumed optimal dose for up to 3 total challenge cohorts: 2A, 2B and 2C.

NOTE: AR is the percentage of participants meeting the pre-defined symptomatic influenza infection definition described in section 4.1.

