#### 8.2.1 Procedures to be Followed in the Event of Abnormal Laboratory Test Values or Abnormal Clinical Findings

The site PI or designated clinician licensed to make medical diagnoses and listed on Form FDA 1572 is responsible for recording all AE/SAEs that are observed or reported during this study, regardless of relationship to study product. AE/SAEs, abnormal laboratory test values or abnormal clinical findings will be collected, assessed, documented, reported, and followed appropriately, using a local laboratory as necessary. In determining eligibility, refer to Section 5.1 and 5.2, and the protocol-specific MOP.

Signs, symptoms, laboratory findings that are part of mild to moderate influenza disease collected as part of the Modified Jackson Score, in addition to mild or moderate fever and lymphopenia from the time of challenge through 7 days post-challenge, will not be considered adverse events (AEs). These signs, symptoms, and laboratory findings (mild and moderate) include the following: runny nose, stuffy nose, sneezing, sore throat, headache, cough, malaise (tiredness), body aches, chills, feverish, shortness of breath, earache, fever, and lymphopenia. Mild to moderate fever is defined in Appendix A and mild to moderate lymphopenia is defined in Appendix B. Influenza infection related symptoms that are deemed by the investigator to be severe, in addition to severe fever as defined in Appendix A and severe lymphopenia as defined in Appendix B, will be considered as adverse events. Symptoms as assessed by the FLU-PRO will not be assessed as adverse events unless deemed by the investigator to be severe.

Safety will be assessed by the frequency and severity of:

- 1. Study product-related serious adverse events occurring from the time of the challenge through the end of the study (approximately 2 months post-challenge).
- 2. Clinical safety laboratory adverse events occurring from the time of challenge through Study Day 8. Parameters to be evaluated include: white blood cells (WBCs), absolute lymphocyte count, hemoglobin, platelets, and alanine transaminase (ALT), and creatinine (Cr).
- 3. Adverse Events non-serious adverse events occurring from the time of challenge through approximately 28 days post-challenge. See below for how adverse events are defined.

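### In halting criterion 4, the count of four per dosing group can never cause a first pause by itself, so one event in each of three cohorts meets neither count

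*Protocol*

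**What the plan says.** Protocol 7.1.1 lists five events that pause enrolment and dosing for SMC review. The fourth has two alternative counts: "Two or more subjects per challenge cohort (or four or more subjects per dosing group) experience the same related grade 3 AE", with events counted through the confinement period.

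The number of cohorts per dose is fixed in Protocol 4.1 (Safety Threshold) and in the table in 6.3.1. The 10^4 group has Cohorts 1A to 1C. The 10^5 group "similarly includes up to three cohorts each with a targeted total of 12 subjects receiving" virus, plus one sham each. The 10^6 group is last, "with each of two challenge cohorts including a targeted total of 17 subjects receiving" virus, again with one sham each.

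The halting criteria also feed the dose decision. Protocol 4.3 makes escalation depend on this condition: "The tested dose is determined to be safe with no occurrence of halting criteria or severe influenza complications". Protocol 9.5.2 uses the halting criteria to define which dose counts as safe when the optimal dose is chosen.

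No section says what the count of four is meant to add to the count of two, or whether counts continue or restart after the SMC clears a pause.

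**The concern.** The only thing a count over a dosing group can add to a count within a cohort is to catch events that accumulate across cohorts. The attack rate (AR) is handled that way: "Cumulatively, if fewer than 80% of subjects in Cohorts 1A, 1B, and 1C meet the case definition for influenza the dose will escalate". The group count in criterion 4 reads like the safety counterpart, but it is set too high to act first.

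As a result, two identical related grade 3 events in one cohort of 12 virus recipients stop the study for independent review. Three spread evenly over 36 recipients at the same dose do not, at least not through criterion 4. The dose could then be kept as optimal, or escalated, without that criterion having sent the pattern to the SMC.

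**Working it through.** **Cohort structure.** Virus recipients: 3×12 + 3×12 + 2×17 = 106. Shams: 3 + 3 + 2 = 8. The total of 114 matches the maximum in Protocol 9.3.2, so three, three and two are the right cohort numbers.

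**Can four act first?** A first pause due to the group count alone needs a total of at least 4 with every cohort at 0 or 1. The largest total with every cohort at 0 or 1 equals the number of cohorts: 3 at 10^4 and 10^5, 2 at 10^6. Enumerating all count patterns for 3×12, 3×13, 2×17, 2×18 and over-enrolled cohorts (3×20) finds none that qualify. This does not depend on event rate, cohort size or how shams are counted. A count of three would act first in exactly one pattern, 1+1+1, and only where there are three cohorts.

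**What four can still do.** In patterns such as 1+1+2 or 0+4 it is met at the same moment as the cohort count and adds nothing. After a cleared pause, and only if counts carry over, it can add a pause in patterns such as 2+1+1, or 3+1 at 10^6. For 3×12 that has probability 3.5% or 11.5% at event risks of 5% or 10%, if the group fills.

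**How likely is 1+1+1?** The documents give no grade 3 rate, so the risk q per virus recipient is an assumption. If all three cohorts of 12 enrol,

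P(1+1+1) = [12q(1−q)^11]^3.

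| q | 12q(1−q)^11 | P(1+1+1) |
|---|---|---|
| 1% | 0.107 | 0.1% |
| 2% | 0.192 | 0.7% |
| 5% | 0.341 | 4.0% |
| 10% | 0.377 | 5.3% |

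The maximum over all q is 5.7%, at q = 1/12.

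**How likely is it that a third cohort enrols?** SAP 4.1 and 5.2 compute the interim AR blinded, over all participants including the sham. The denominators are therefore 13, 26 and 39. Counting the sham as a non-case, the cumulative cases needed to stay at the dose are 11, 21 and 32 for the 80% threshold (10.4, 20.8 and 31.2 rounded up), and 10, 19 and 28 for the 70% threshold (9.1, 18.2 and 27.3 rounded up). Binomial sums over 12 virus recipients per cohort give:

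| Dose, true AR | Reach third cohort | then escalate | then keep dose |
|---|---|---|---|
| 10^4, 80% | 17.0% | 8.8% | 8.2% |
| 10^5, 70% | 14.6% | 4.7% | 9.9% |

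The 10^5 row is conditional on the study having moved to 10^5.

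**Joint probabilities** (product, treating events as independent of the AR), at q = 5% or 10%:

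- 10^4, AR 80%: 0.170 × 0.0397 = 0.7%, or 0.170 × 0.0534 = 0.9%. With escalation as well: 0.35% or 0.47%.
- 10^5, AR 70%: 0.146 × 0.0397 = 0.6%, or 0.146 × 0.0534 = 0.8%. With escalation as well: 0.19% or 0.25%.

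If the true AR at 10^5 is 80%, the joint chance of reaching the third cohort rises to 1.9% or 2.6%. Using 12 virus recipients as denominator instead gives 1.5% or 2.1% for the 10^4 scenario and 1.6% or 2.2% for the 10^5 scenario. Over true ARs of 60% to 80% and both denominators, the joint chance of 1+1+1 followed by escalation never exceeds 0.48%.

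**The case against.** The strongest reply is that this is redundancy, not lost protection. The cohort count is the stricter rule and is untouched, and nothing in the protocol says the group count was meant to act first. That stands: its purpose is inferred from its form.

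A reader might go further and infer that accumulating grade 3 events could escape oversight. The documents do not support that. The internal safety review committee (ISRC) reviews safety events after every cohort (Protocol 10.1.6). Criterion 5 allows a halt for any medically significant issue. Protocol 4.1 treats "the occurrence of severe influenza complications in any study subject" as crossing the safety threshold, and related serious events in confinement fall under criterion 3. Protocol 6.3.3 adds: "The SMC will receive data in aggregate by cohort and challenge dose group". The SMC can also meet ad hoc and reviews cumulative unblinded data at the end. Its charter is not among the documents and may already cover cumulative counts. These safeguards are discretionary or address other events, so they reduce the consequence without making the count work.

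Two other strong readings also fail. One is that the group count is wholly dead; it has a re-trigger role if counts carry over. The other is that 10^6 has the same gap; Cohort 3B is the last, so no later cohort remains to pause. That second point applies in part at the lower doses too. When the third cohort ends with the dose kept, about half of third-cohort paths at 10^4 and two thirds at 10^5 in the scenarios above, no further cohort follows.

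Finally, how many events to tolerate is a clinical choice. Under Protocol 8.2.1, "Influenza infection related symptoms that are deemed by the investigator to be severe" are themselves adverse events, so some grade 3 events are expected. This argues for a modest remedy and also means that independence of events and AR is only a working assumption.

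**Conclusion.** The structural point is certain: at no dose can four per dosing group by itself cause a first pause. It can add a pause only after SMC clearance and only with carry-over, on which the protocol is silent; if counts restart, it adds nothing. The one pattern of three or more events at a dose that meets neither count is 1+1+1 at 10^4 or 10^5.

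The practical impact is small. With all three cohorts enrolled, the pattern's probability runs from 0.1% to 5.3% over the assumed risks of 1% to 10%, with a peak of 5.7%. Jointly with reaching the third cohort it is about 0.6% to 0.9% at risks of 5% to 10% in the two main scenarios, and lower at smaller risks. Escalation follows in under 0.5%. These sizes rest on assumed event risks, assumed true ARs, the sham counted as a non-case, and independence of events and AR. This is an optional clarification of low priority.

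**What to change.** In Protocol 7.1.1, for a first pause at 10^4 and 10^5, set the dosing-group count to three or more subjects with the same related grade 3 event, tallied cumulatively over the cohorts of that dose at each ISRC review. State that counts carry over after SMC clearance and that four or more per dosing group remains the count for a further pause after a cleared one. Leave 10^6 unchanged. Align the SMC charter if needed.

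Keeping four after a cleared pause matters. With three throughout, patterns 2+1, 2+0+1 and 0+2+1 would pause the study again at the third subject. Writing f_k for the binomial probability of k events among 12, the probability is f_2·f_1 + 2·f_2·f_0·f_1 = 7.0% at q = 5% and 13.6% at q = 10%, if all three cohorts enrol and the SMC clears the first pause. That exceeds the pattern being targeted.

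The change needs no added subjects or procedures. Its cost is an occasional extra ad hoc SMC review in the 1+1+1 pattern. The SAP describes parts of the conduct in the past tense. If dosing is complete, the wording belongs in later protocols of this design, and the study report can show same-event grade 3 counts cumulatively by dose.
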